#### 13.5 Sample Size and Power

As this is a pilot trial, the sample size was determined based on feasibility and logistical considerations rather than on power for hypothesis testing. We aim to enroll 26 evaluable patients per oxybutynin arm and 13 evaluable patients per placebo arm (i.e., 78 evaluable patients total). For the primary aim, 26 evaluable patients per oxybutynin arm and 13 evaluable patients per placebo arm with 6 weekly hot flash scores provide 76% power to detect a mean difference in hot flash score reduction from baseline when comparing each oxybutynin arm (5.0 mL twice daily or 2.5 mL twice daily to the placebo arm (both placebo arms combined) based on a two-sided *t*-test estimated via a mixed model, nominal significance level of  $\alpha = .10$ , intraclass correlation of .50, and population standardized mean difference of 0.50 (i.e., Cohen's convention for a moderate effect size)[44]. In a similar study in women, Cohen's *d* equaled 0.85 when comparing the higher dose oxybutynin arm (2.5 mL twice daily escalated to 5.0 mL twice daily) to the placebo arm [45]. An additional 9 patients will be accrued to account for a 10% loss in sample size due to ineligibility, major treatment violation, or cancellation. Maximum projected accrual is, therefore, 87 patients.

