#### **13.0 STATISTICAL CONSIDERATIONS**

#### 13.1 Overview

This randomized four-arm, double-blind, placebo-controlled phase II trial will assess the efficacy and safety of oxybutynin for reducing hot flash scores in men receiving androgen deprivation therapy. The primary endpoint of this phase II trial is hot flash scores at 6 weeks post-randomization. All analyses will follow an intent-to-treat approach that includes all randomized patients who meet eligibility criteria.

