#### 13.4 Analysis Plan

**To assess efficacy**, a mixed model will be estimated that includes baseline and weekly hot flash scores across the 6-week treatment period. The mixed model will include a fixed intercept; fixed effect for time, arm, and arm by time interaction; and residual covariance matrix based on the observed covariances. Alternative structures will be investigated for the residual covariance matrix, with final selection based on convergence of the mixed model and minimization of the Akaike information criterion. Stratification factors used in the randomization as well as baseline patient characteristics and prognostic factors may be included in the mixed model as covariates if imbalances across arms occur. For this mixed model, time will be treated as nominal (not continuous), such that the mixed model will not be making assumptions about the trajectory of

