patients' hot flash scores over time. Estimates from the mixed model will be used to construct 90% confidence intervals for mean differences in hot flash score reduction from baseline to 6 weeks post-randomization between the oxybutynin and placebo arms (i.e., Arm A versus Arms C and D combined; Arm B versus Arms C and D combined). To control the Type I error rate, a fixed sequence procedure will be employed such that the following two tests will be sequenced rather than conducted simultaneously. Hot flash score reduction from baseline to 6 weeks will be compared across patients assigned to oxybutynin at 5.0 mL twice daily (Arm B) and patients assigned to placebo (Arms C and D combined) using a contrast estimated via the mixed model. The contrast will involve a two-sided t-test with a nominal significance level of  $\alpha = .10$ . If and only if this test is significant, hot flash score reduction from baseline to 6 weeks will be formally compared across patients assigned to oxybutynin at 2.5 mL twice daily (Arm A) and patients assigned to placebo (Arms C and D combined) using a second contrast estimated via the mixed model. This contrast will also involve a two-sided *t*-test with a nominal significance level of  $\alpha = .10$ . The proposed sequencing is based on the assumption that the effect of oxybutynin will increase monotonically with respect to dose. If p < .10 for both tests, we will conclude that both dosing schedules significantly improved hot flash scores at 6 weeks relative to placebo. If  $p \le .10$  for the first test but p > .10 for the second test, we will conclude that the higher dosing schedule significantly improved hot flash scores at 6 weeks relative to placebo but that the lower dosing schedule did not significantly improve hot flash scores at 6 weeks relative to placebo. Finally, if p > .10 for the first test, we will conclude that neither dosing schedule significantly improved hot flash scores at 6 weeks relative to placebo. In practice, if p > .10 for the first test, we will still conduct the second test, but as an exploratory analysis rather than as a primary analysis. We will also conduct a responder analysis at 6 weeks comparing the proportion of patients who experience a clinically significant improvement in hot flash scores since baseline across the oxybutynin and placebo arms using Fisher's exact test,  $\chi^2$  test, or logistic regression. Stratification factors used in the randomization as well as baseline patient characteristics and prognostic factors may be included in the logistic regression model as covariates if imbalances across arms occur. A clinically significant improvement will be defined as a 50% or greater reduction in hot flash scores since baseline based on preliminary evidence suggesting that patients consider a 50% or greater reduction in frequency of moderate to severe hot flashes to be a meaningful improvement.[41, 42] Patients who experience a 50% or greater reduction in hot flash scores since baseline will be deemed responders, while the remaining patients (including those with missing hot flash scores) will be deemed non-responders. As an exploratory analysis, we will investigate whether these efficacy results differ when using a single day rather than a full week to define patients' baseline hot flash scores.

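### Section 13.5 states 76% power, but the week-6 change contrast that Section 13.4 tests has about 56% under the stated inputs

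*Combined protocol and SAP*

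**What the plan says.** Section 13.1 sets the time point: "The primary endpoint of this phase II trial is hot flash scores at 6 weeks post-randomization".

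Section 13.4 describes the analysis: "a mixed model will be estimated that includes baseline and weekly hot flash scores across the 6-week treatment period". The fixed effects are time, arm and arm by time, and "time will be treated as nominal (not continuous), such that the mixed model will not be making assumptions about the trajectory of" the scores. The first of two sequenced tests, two-sided at .10, is set out as "Hot flash score reduction from baseline to 6 weeks will be compared across patients assigned to oxybutynin at 5.0 mL twice daily (Arm B") and the two placebo arms combined. For the 2.5 mL arm, "If and only if this test is significant, hot flash score reduction from baseline to 6 weeks will be formally compared". If the first test fails, "we will conclude that neither dosing schedule significantly improved hot flash scores at 6 weeks relative to placebo".

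Section 13.5 then says that the planned numbers, with 6 weekly scores, "provide 76% power to detect a mean difference in hot flash score reduction from baseline when comparing each oxybutynin arm". The inputs are a two-sided t-test from a mixed model, alpha .10, intraclass correlation .50 and a standardized mean difference of 0.50. The sentence names no week and does not say which SD standardizes the difference. The same section states that "the sample size was determined based on feasibility and logistical considerations rather than on power for hypothesis testing".

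**The concern.** The power sentence is offered for the primary aim but does not identify the contrast. Its mention of six weekly scores and an intraclass correlation suggests that the weekly scores are pooled to gain precision. The primary test in Section 13.4 does not pool them: it is a single contrast at week 6 against baseline, from a model whose means are free at every visit in every arm. Under those conditions the intermediate weeks should not help, and 76% looks too high.

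The figure affects how a non-significant result is read. The plan attaches a formal negative conclusion for both doses to a failed 5.0 mL test. A reader who believes that the test had 76% power at a moderate effect will take that conclusion as stronger evidence against benefit than it is, and could carry the error into the decision on a phase III trial.

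**Working it through.** **Inputs.** All are from Section 13.5 except the pooling and the contrast: n = 26 per oxybutynin arm; placebo 13 + 13 = 26 (pooled under Section 13.2); d = 0.50; correlation ρ = .50; two-sided α = .10; 6 weekly scores. Contrast and mean model: Section 13.4. Assumptions added here: complete data, compound symmetry, and ρ read as the common correlation between any two visits, baseline included. Variances are in units of the single-visit variance σ².

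**Power formula.** Noncentrality = d / √(v × 2/26), where v is the per-patient variance of the contrast. The t results use 50 df (two arms) and 75 df (three arms).

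**1. Reproducing 76%.** Average the six treatment weeks, with the same effect of 0.50 at each:
- v = (1 + 5 × 0.5)/6 = 0.583
- noncentrality = 0.5/√(0.583 × 2/26) = 2.36
- power = 75.3% to 75.6% (t); 76.3% (normal)

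Subtracting baseline from that average leaves v unchanged at this correlation: 0.583 + 1 − 2 × 0.5 = 0.583. The phrase about reduction from baseline therefore does not separate the two. Averaging seven points, v = (1 + 6 × 0.5)/7 = 0.571, gives 76.0% to 76.4% (t). The exact origin of the 76% cannot be identified from the document.

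**2. The planned contrast.** With a separate mean for every arm and visit and no missing data, the mixed-model estimate of the week-6-minus-baseline arm difference is the simple difference in mean change. The other five weeks drop out.
- v = 1 + 1 − 2 × 0.5 = 1.0
- noncentrality = 0.5/√(1.0 × 2/26) = 1.80
- power = 55.3% to 55.7% (t); 56.3% (normal)

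Simulation with 20,000 trials, seven visits and compound symmetry .50 gave 55.4% to 55.6% for this contrast and about 76% for the six-week average. The rejection rate under the null was 10.2%.

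**3. Baseline adjusted or constrained.** Section 13.4 does not specify this. v = 1 − 0.5² = 0.75 gives 65.9% to 66.2% (t); 66.9% (normal).

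**4. Sensitivity to the correlation.** With d on the single-visit SD, v = 2(1 − ρ), 75 df:

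| Baseline-to-week-6 correlation | Power |
|---|---|
| 0.4 | 49.5% |
| 0.5 | 55.7% |
| 0.6 | 63.8% |
| 0.7 | 74.6% |

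Reaching 76% needs a correlation of about 0.71. If d is on the change-score SD, power is 56% at any correlation. At ρ = .50 the two scales coincide.

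**5. Sensitivity to the effect.** About d = 0.66 gives 76% with 26 per group. At d = 0.50, 76% would take about 45 per group (normal approximation). At the 0.85 that Section 13.5 cites from the women's trial, power is about 92%. That 0.85 appears to be on the change-score SD. Section 1.2 gives mean changes of −16.9 (SD 15.6) and −5.7 (SD 10.2) for the same trial. The difference of 11.2, divided by √((15.6² + 10.2²)/2) = 13.18, is 0.85, assuming equal arm sizes for pooling.

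**6. The testing sequence.** The two tests share the placebo group, so their correlation is 0.5. The chance of formal success on both doses (5.0 mL, 2.5 mL) is about 39% at effects of 0.50 and 0.50, and about 54% at 0.85 and 0.50.

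**The case against.** Five points deserve an answer.

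- **No slip in calculation.** The 76% can be reproduced as the power of a different contrast. That is right, and the fault is a mismatch between two sections. It still leaves a figure, stated for the primary aim, that the primary test does not have.
- **A feasibility-sized pilot.** The sample size does not rest on power, and the 90% confidence intervals planned in Section 13.4 will inform readers better than planning power can. Both points stand. They limit the consequence to one sentence and its reading, but do not make the sentence correct.
- **The true effect may be larger.** At 0.85 the risk of missing the 5.0 mL effect is only about 8%. This is fair and belongs in the restated text. The 44% applies at 0.50, which is the protocol's own planning value.
- **The inputs are interpreted.** Section 13.5 does not say that its intraclass correlation is the baseline-to-week-6 correlation, and Section 13.4 leaves the covariance structure open. This also stands, and the table shows how far it matters. With d on the single-visit SD, a correlation near 0.7 would bring power close to 76%, but the only value stated is .50. The authors should confirm what it refers to.
- **Per-comparison power is openly stated.** Section 13.5 speaks of each oxybutynin arm, and Section 13.4 sets out the sequence in full. The joint figures are therefore an optional addition. They depend on assumed effect pairs and correct nothing that the plan claims.

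**Conclusion.** The point holds. Under the inputs in Section 13.5, the week-6 change contrast that Section 13.4 makes primary has about 56% power per comparison, roughly 20 percentage points below the stated 76%. Adjusting for baseline or constraining baseline means would raise it to about 66%, still about 10 points short. At a standardized difference of 0.50, the chance of a non-significant 5.0 mL test is about 44% rather than 24%.

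This rests on complete data, compound symmetry and a correlation of .50 that includes baseline. The shortfall does not depend on knowing how 76% was obtained. The error should be corrected because a formal conclusion about both doses follows from the first test. It does not call the sample size or the analysis into question.

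**What to change.** Keep the week-6 contrast and restate the power sentence in Section 13.5, for example:

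> For the arm difference in change from baseline to week 6 (26 versus 26 evaluable patients, two-sided alpha .10, standardized mean difference 0.50, baseline-to-week-6 correlation .50), power is about 56% per comparison, and about 92% at a standardized mean difference of 0.85. The 2.5 mL comparison is formal only if the 5.0 mL comparison is significant.

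Also:
- State which SD scales the standardized difference, and confirm that .50 is meant as the baseline-to-week-6 correlation.
- Quote about 66% only if Section 13.4 is reworded to adjust for baseline or to constrain baseline arm means.
- If joint power is reported, give a range with its assumed effects (about 39% at 0.50 and 0.50; about 54% at 0.85 and 0.50).

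Making the six-week average the primary contrast would also bring the power figure and the test into line. That would change the primary endpoint in Section 13.1 and both tests in Section 13.4, and is not needed to correct the statement.

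The cost is wording in Section 13.5 and a less favourable stated power. The sample size, primary contrast, testing sequence and data collection do not change.

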#### 13.2 Study Design

Patients will be randomly assigned to oxybutynin at 2.5 mL twice daily, oxybutynin at 5.0 mL twice daily, placebo at 2.5 mL twice daily, or placebo at 5.0 ml twice daily in a 2:2:1:1 ratio according to the dynamic allocation scheme. Stratification factors will include daily hot flash frequency at baseline (4 to 9 hot flashes per day versus 10 or more hot flashes per day), hot flash duration at baseline (less than 9 months versus 9 or more months), and number of prior hot flash therapies (0 versus 1 or more). The study design includes two placebo arms to match the dose of the two oxybutynin arms; however, patients randomized to the two placebo arms will be combined to form a single placebo arm for analysis. All analyses will follow an intent-to-treat approach that includes all randomized patients who meet eligibility criteria.

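### Section 13.5 gives 76% power for each oxybutynin arm, but under the fixed sequence in Section 13.4 a formal conclusion for 2.5 mL has about 63% power when both effects are 0.50

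*Combined protocol and SAP*

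**What the plan says.** Section 13.5 reports a single power figure under the primary aim. The planned numbers are given as "We aim to enroll 26 evaluable patients per oxybutynin arm and 13 evaluable patients per placebo arm", and Section 13.2 adds that "patients randomized to the two placebo arms will be combined to form a single placebo arm for analysis", so each contrast is 26 against 26. These numbers, with six weekly scores per patient, "provide 76% power to detect a mean difference in hot flash score reduction from baseline when comparing each oxybutynin arm" with combined placebo. Both doses are named there. The test is "based on a two-sided *t*-test estimated via a mixed model" at a nominal two-sided .10, and the remaining inputs are "intraclass correlation of .50, and population standardized mean difference of 0.50". No separate effect size is given for either dose.

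Section 13.4 sets the order of testing. The 5.0 mL arm is compared with placebo first. For 2.5 mL the rule is: "If and only if this test is significant, hot flash score reduction from baseline to 6 weeks will be formally compared". The conclusion that both doses work requires both rejections: "If p < .10 for both tests, we will conclude that both dosing schedules significantly improved hot flash scores". If the first test fails, the plan concludes that neither schedule improved scores, and the 2.5 mL test is run as exploratory only. The order is justified by an assumption that the effect rises with dose.

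Section 13.5 does not mention the sequence. It does say that the sample size was set on feasibility rather than on power.

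**The concern.** The power statement covers both doses alike, but the testing rule does not treat them alike. The 5.0 mL comparison stands on its own. The 2.5 mL comparison can support a primary conclusion only when the 5.0 mL comparison has already succeeded. Its chance of doing so is the joint probability of two rejections, which cannot exceed the power of either test and is below 76% whenever the first test can fail while the second would have rejected.

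The primary objective in Section 2.1 concerns two doses, and Section 13.4 contemplates a phase III trial. A reader who takes 76% as the chance that this design can formally establish the lower dose would expect more than it delivers under its own inputs.

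**Working it through.** **Inputs.** 26 per oxybutynin arm and 13 + 13 = 26 on placebo; six weekly scores; intraclass correlation 0.50; standardized difference 0.50 (all Section 13.5). Two-sided alpha .10, critical value 1.645. Fixed sequence, 5.0 mL then 2.5 mL (Section 13.4).

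**Step 1: reproduce the 76%.** In units of the standard deviation of one weekly score:

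- SD of the mean of six weekly scores = √((1 + 5 × 0.5)/6) = √0.583 = 0.764. Subtracting a baseline score with the same correlation leaves it unchanged: 0.583 + 1 − 2 × 0.5 = 0.583.
- Standard error of the difference = 0.764 × √(2/26) = 0.212.
- Non-centrality = 0.50/0.212 = 2.360.
- Power = Φ(2.360 − 1.645) = 76.3%. With a noncentral t it is 75.6% on 75 df and 75.3% on 50 df.

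The plan's figure is thus the power of one unconditional comparison.

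**Step 2: correlation of the two contrasts.** Both use the same placebo mean. Their covariance is σ²/26 and each variance is 2σ²/26, so the correlation is 0.5.

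**Step 3: probability that both tests reject, 0.50 for each dose.**

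- Bivariate normal, both means 2.360, correlation 0.5: P(both > 1.645) = 63.7%.
- Non-centrality set to give exactly 76% (0.706 + 1.645 = 2.351): 63.3%.
- 400,000 simulated pairs of t-tests with pooled variance on 75 df: 75.6% for one test, 63.0% for both.
- Bounds: 0.763² = 58.2% if the tests were independent; 76.3% if perfectly correlated.

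The loss is 76 − 63 = 13 points.

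**Step 4: unequal effects.** These effect sizes are assumptions, except that 0.85 is the higher-dose value Section 13.5 cites from the study in women. The method is that of Step 3.

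| 5.0 mL effect | 2.5 mL effect | Power, 5.0 mL test | Power, formal 2.5 mL claim |
|---|---|---|---|
| 0.50 | 0.50 | 76.3% | 63.7% |
| 0.60 | 0.50 | 88.3% | 71.0% |
| 0.70 | 0.50 | 95.2% | 74.5% |
| 0.85 | 0.50 | 99.1% | 76.1% |
| 0.50 | 0.40 | 76.3% | 51.9% |
| 0.50 | 0.30 | 76.3% | 37.1% |

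**Step 5: dependence on the single-test figure.** Step 1 needs the six weekly scores to be averaged. The contrast in Section 13.4 is baseline to week 6. For a week-6 change alone, without borrowing across weeks, the SD is √(2 × (1 − 0.5)) = 1 and the non-centrality is 0.50/√(2/26) = 1.803. One test then has 56.3% power and the pair 39.8%.

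**Step 6: the 2.5 mL test once opened.** Given that the 5.0 mL test has rejected, the chance that the 2.5 mL test also rejects is 0.633/0.76 = 83%.

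**The case against.** The strongest reply is that nothing in Section 13.5 is miscalculated. Its wording is per comparison: one t-test, a nominal level, one arm against placebo. It claims no power for the sequential procedure. That stands: a reader might infer that the 76% is an arithmetical error, and Step 1 shows that it is not. What is missing is the figure for the second step, in a sentence that presents one number for both doses under the primary aim.

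A second reply is that the 13-point gap belongs to the equal-effects case, whereas Section 13.4 assumes an effect that rises with dose. This is fair, and Step 4 shows the gate costing almost nothing at 0.85. But equal effects of 0.50 are what Section 13.5 itself uses. A monotone pattern also does not guarantee a small loss relative to 76%: with 5.0 mL at 0.50 and 2.5 mL lower, the chance of a formal 2.5 mL claim falls further.

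A third reply is that the sample size rests on feasibility. This limits the consequence, since no decision about numbers turns on the figure, but it does not make the published figure describe the second dose.

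A reader might also infer that a failed 2.5 mL test would come from a test with only 63% power. The documents do not support that. Once formally opened, the test has about 83% conditional power under the same inputs. If the gate stays shut, the exploratory test is still run, and its unconditional power remains 76%.

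**Conclusion.** The point holds as a gap in the power statement. The 76% is right per comparison and for the 5.0 mL test. The chance of a formal 2.5 mL conclusion is about 63% (63.0% to 63.7% by method) under the plan's own inputs. That result rests on an effect of 0.50 for both doses, 26 evaluable patients in each of the three analysis groups, a contrast correlation of 0.5 from the shared placebo group, and averaging of the six weekly scores. If the 5.0 mL effect is larger, the loss shrinks towards nothing. If the single-test figure is restated for the week-6 contrast, both numbers change, so 63% is not a lower bound. The 63% is the probability of a formal claim for 2.5 mL and should not be read as the power of that test in isolation. The correction is worth making, but it concerns reporting and does not question the design.

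**What to change.** In Section 13.5:

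1. State that 76% is per-comparison power and applies to the 5.0 mL test.
2. State that, under the fixed sequence in Section 13.4, the power to formally declare 2.5 mL effective is about 63% when both effects are 0.50.
3. Add a line for the monotone case: with 2.5 mL at 0.50, about 71% if the 5.0 mL effect is 0.60, 75% if 0.70 and 76% if 0.85.
4. Recompute all of these if the single-test figure is revised for the baseline-to-week-6 contrast.

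The cost is two or three sentences and a less favourable stated figure for the lower dose. Sample size, alpha, testing order and decision rules stay as they are.
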